7.2.5. Statistical Analyses / Methods

Details of the planned displays are provided in [Appendix 13: List of Data Displays](#) and will be based on GSK data standards and statistical principles.

[Table 4](#) provides an overview of the planned efficacy analyses. Details of the planned displays are provided in [Appendix 13: List of Data Displays](#) and will be based on GSK data standards and statistical principles.

Table 4 Overview of Planned Secondary Efficacy Analyses

Endpoints	Stats Analysis			Summary		Individual	
	T	F	L	T	F	F	L
Proportion of Participants with Plasma HIV-1 < 50 c/mL at Week 48 – Snapshot^[1]							
Key secondary analysis	Y ^[2]			Y ^[2, 3]	Y		Y ^[3]
Treatment Heterogeneity across randomization strata	Y						
Proportion of Participants without efficacy-related discontinuation (ERDF) or treatment-related discontinuation (TRDF) failure (refer to Section 13.6.4)							
Kaplan-Meier estimate				Y			
Proportion of Subjects with Plasma HIV-1 RNA ≥50 copies/mL over time through Week 48– Snapshot							
by Visit				Y	Y ^[4]		
by Visit and Subgroup ^[5]				Y	Y		

Endpoints	Stats Analysis			Summary		Individual	
	T	F	L	T	F	F	L
Proportion of Subjects with Plasma HIV-1 RNA <50 copies/mL over time through Week 48– Snapshot							
by Visit				Y	Y ^[6]		
by Visit and Subgroup ^[5]				Y	Y ^[7]		
Proportion of Subjects with Plasma HIV-1 RNA <200 copies/mL over time through Week 48– Snapshot (also for ≥200 copies/mL)							
by Visit				Y ^[8]	Y ^[9]		
Proportion of Subjects with Plasma HIV-1 RNA <50 copies/mL at Week 48 by delay in IP injection^[10] - Snapshot (exploratory analysis)							
by Delay in IP injection				Y			Y
Proportion of Subjects with Plasma HIV-1 RNA <2 copies/mL (exploratory analysis)							
by Visit - Observed Case Analysis				Y			Y

1. This analysis will be performed using the similar approach as described for the primary analysis in Section 7.1.5.1
2. Generated using the 'Intent-to-Treat Exposed' (primary) and 'Per-Protocol' (sensitivity) populations.
3. Study outcomes (i.e., response below 50 c/mL, 'HIV-1 RNA≥50' or reason for no data in the window) based on the snapshot algorithm.
4. Line plots, with 95% confidence intervals(CIs), for the proportion of subjects HIV-1 RNA ≥50c/mL for overall and by treatment group at each visit. The 95% CIs will be calculated using Exact (Clopper-Pearson) confidence interval if the proportion is 0%. Otherwise, they are derived using the normal approximation.

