- For Current ART arm, missing IP discontinuation Date will be imputed, for purposes of calculating exposure, as the date of last visit or the recorded date of withdrawal/completion, whichever is earlier.

Adherence to CAB/RPV Injection Schedule

Timeliness of Injections Relative to Date of Projected Dosing Visits are assessed by using "actual injection visit date - projected visit date from Week 4B". Each injection visit is counted only once. Individual CAB and RPV injections administered at the same visit are not counted twice. "Extra" unscheduled injections are excluded from all derivations. For example, if during a scheduled visit a subject receives 1 ml of injection instead of 2 ml due to a dosing error, but returns one week later for the remaining 1 ml injection, then the additional visit is excluded. If a subject receives an extra injection at an unscheduled visit by mistake, this visit will also be excluded.

The categories of Timeliness of Injections Relative to Date of Projected Dosing Visits for summary are listed below:

- < -14 days
- 14 to - 8 days
- 7 to - 4 days
- 3 to -2 days -1
- 0 day
- 1
- 2 to 3 days
- 4 to 7 days
- 8 to 14 days
- >14 days
- Missed Injection without Oral Bridging
- Missed Injection with Oral Bridging

Corrected QTC

When not entered directly in the eCRF, corrected QT intervals by Bazett's (QTcB) and Fridericia's (QTcF) formulas will be calculated, in msec, depending on the availability of other measurements.

If RR interval (in msec) is provided then missing QTcB and/or QTcF will be derived as

$$QTcB = \frac{QT}{\sqrt{RR/1000}} \qquad QTcF = \frac{QT}{\sqrt[3]{RR/1000}}$$

where uncorrected QT interval is also measured in msec.

If RR interval is not provided directly and one of QTcB or QTcF has been entered, then RR interval can be obtained from the above formulas and used to calculate the other correction method value; i.e.,

$$QTcB = \sqrt{\frac{QTcF^3}{QT}} \qquad QTcF = \sqrt[3]{QT \cdot QTcB^2}$$

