- If a subject with CDC 'Stage II' at baseline had the lowest post-baseline CD4+ =220 cell/mm³ AND had at least one new AIDS-defining condition, then HIV disease progression for this subject would be considered as 'CDC stage II at baseline to CDC stage III'.

Delay in IP Injection

IM dosing is expected to occur every 4 weeks from Week 4b onwards. The Delay in IP injection (days) will be calculated as below:

- Delay in IP injection(days) = Injection date - date of preceding injection – 28 days

Delay in IP injection will be grouped into: ≤1, 2-3, 4-7, >7 days.

The proportion of subjects with HIV-1 RNA ≥50 c/mL at Week 48 (Snapshot) will be summarized by last delay in IP Injection. The last delay in IP injection will be the delay in IP injection at Week 48, or the delay in last IP injection prior to Week 48 if a subject does not receive Week 48 injection (i.e. missing visit or withdrawal).

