2.15	ITT-E	Shell TSEF7.1	Summary of Kaplan-Meier Estimates of Proportion of Subjects Without Confirmed Virologic Failure by Week 48 during Maintenance Phase - Efficacy Related Discontinuation = Failure		WK48
2.16	ITT-E	Shell TSEF2	Proportion of Subjects with Plasma HIV-1 RNA <50 c/mL by Visit (Maintenance Phase) – Snapshot Analysis		WK48
2.17	ITT-E	Shell TSEF2	Proportion of Subjects with Plasma HIV-1 RNA <50 c/mL by Subgroup and Visit (Maintenance Phase) – Snapshot Analysis		WK48
2.18	ITT-E	Shell TSEF2	Proportion of Subjects with Plasma HIV-1 RNA <200 c/mL by Visit (Maintenance Phase) – Snapshot Analysis		WK48
2.19	ITT-E	Shell TSEF9	Proportion of subjects with HIV-1 RNA \geq 50 c/mL at Week 48 (Snapshot) by Last Delay in IP Injection (Maintenance Phase)	For Q4W IM arm only. The last delay in IP injection is the delay in IP injection at Week 48, or delay in last IP injection prior to Week 48 if a subject has no injection at WK48 (e.g. missing visit or early withdrawal)	WK48,
2.20	ITT-E	Shell TSEF8	Summary of Plasma HIV-1 RNA by Visit		WK48, 96, EOS

CONFIDENTIAL

201585

Efficacy: Tables					
No.	Population	IDSL / TST ID / Example Shell	Title	Programming Notes	Deliverable
2.21	ITT-E	Shell TSEF3	Proportion of Subjects Meeting Confirmed Virologic Failure Criteria by Visit (Maintenance Phase)		HL, WK48
2.22	ITT-E	Shell TSEF3	Proportion of Subjects Meeting Confirmed Virologic Failure Criteria by Visit for Q4W Arm Only (Maintenance + Extension Phase)		WK96, EOS
2.23	ESP	Shell TSEF3	Proportion of Subjects Meeting Confirmed Virologic Failure Criteria by Visit for Current ART Arm Only (Extension Phase)		WK96, EOS
2.24	CVF	Shell TSEF4	Summary of Plasma HIV-1 RNA Results at Suspected and Confirmation of Confirmed Virologic Failure – Maintenance phase		WK48
2.25	ITT-E	Shell TSEF5	Summary of Change from Baseline in CD4+ Cell Count (cells/mm ³) by Visit (Maintenance Phase)		WK48, 96, EOS
2.26	ITT-E	Shell TSEF5	Summary of CD4+ Cell Count (cells/mm ³) by Visit (Maintenance Phase)		WK48, 96, EOS
2.27	ITT-E	Shell TSEF5	Summary of CD8+ Cell Count (cells/mm ³) by Visit (Maintenance Phase)		WK48, 96, EOS
2.28	ITT-E	Shell TSEF5	Summary of Change from Baseline in CD8+ Cell Count (cells/mm ³) by Visit (Maintenance Phase)		WK48, 96, EOS
2.29	ITT-E	Shell TSEF5	Summary of CD4+/CD8+ Ratio Cell Count (cells/mm ³) by Visit	While both CD4+ and CD8+ are available on the same date	WK48, 96, EOS

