13.13.14. Pharmacokinetic / Pharmacodynamic Figures

Pharmacokinetic / Pharmacodynamic: Figures					
No.	Population	IDSL / TST ID / Example Shell The similar outputs below from study 200056 (week48idsl)	Title	Programming Notes	Deliverable [Priority]
Last trough/Nominal Week-8 trough CAB/RPV concentration/parameters and efficacy measures					
5.1.	PK	Shell FPK01/Figure 11.1004	Scatter Plot of Last Trough CAB PK Concentration by Snapshot 'HIV-1 RNA≥50' and non-'HIV-1 RNA≥50 c/mL' at Week 48		WK48

Pharmacokinetic / Pharmacodynamic: Figures					
No.	Population	IDSL / TST ID / Example Shell The similar outputs below from study 200056 (week48idsl)	Title	Programming Notes	Deliverable [Priority]
5.2.	PK	Shell FPK01/Figure 11.1005	Scatter Plot of Last Trough RPV PK Concentration by Snapshot 'HIV-1 RNA \geq 50' and non 'HIV-1 RNA \geq 50 c/mL' at Week 48		WK48
5.3.	PK	Shell FPK01/Figure 11.1004	Scatter Plot of Week-8 Trough CAB PK Concentration by Snapshot 'HIV-1 RNA \geq 50' and non-'HIV-1 RNA \geq 50 c/mL' at Week 48		WK48
5.4.	PK	Shell FPK01/Figure 11.1005	Scatter Plot of Week-8 Trough RPV PK Concentration by Snapshot 'HIV-1 RNA \geq 50' and non 'HIV-1 RNA \geq 50 c/mL' at Week 48		WK48
5.5.	PK	Figure 11.1006	Scatter Plot of Delay in last IP injection by Last Trough CAB Concentration at Week 48 at Maintenance phase	Different symbols for Snapshot Non- 'HIV-1 RNA \geq 50' and 'HIV-1 RNA \geq 50'. X axis represents last trough CAB concentration, Y axis indicates Delay in last IP injection (Days)	WK48

Pharmacokinetic / Pharmacodynamic: Figures					
No.	Population	IDSL / TST ID / Example Shell The similar outputs below from study 200056 (week48idsl)	Title	Programming Notes	Deliverable [Priority]
5.6.	PK	Figure 11.1006	Scatter Plot of Delay in last IP injection by Last Trough RPV Concentration at Week 48 at Maintenance phase	Different symbols for Snapshot Non- 'HIV-1 RNA \geq 50' and 'HIV-1 RNA \geq 50'. X axis represents last trough RPV concentration, Y axis indicates Delay in last IP injection (Days)	WK48
5.7.	PK	Figure 11.1002	Individual CAB trough concentration-time Profiles for subjects with Snapshot HIV-1 RNA \geq 50 c/mL at Week 48 with Median, 5th & 95th percentile of CAB Conc-Time Profiles for other subjects (Semi-Log)		WK48
5.8.	PK	Figure 11.1003	Individual RPV trough concentration-time Profiles for subjects with Snapshot HIV-1 RNA \geq 50 c/mL at Week 48 with Median, 5th & 95th CAB Conc-Time Profiles for other subjects (Semi-Log)		WK48

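### The exploratory injection-delay display can file a missed, uncovered Week 48 injection as on time and an orally bridged gap as more than 7 days late

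*SAP*

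**What the plan says.** Section 13.6.4 defines the variable as "Delay in IP injection(days) = Injection date - date of preceding injection – 28 days" and sets four groups: "Delay in IP injection will be grouped into: ≤1, 2-3, 4-7, >7 days". The value used is the delay at Week 48, "or the delay in last IP injection prior to Week 48 if a subject does not receive Week 48 injection"; a missing visit and a withdrawal are the SAP's own examples. The programming note to Table 2.19 (section 13.13.5) repeats the rule and limits the table to the Q4W IM arm. Neither place mentions oral bridging.

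Other sections do treat missed or bridged dosing separately:

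- The adherence summary in 13.6.2 has a category "Missed Injection without Oral Bridging" and a matching one with bridging.
- The Per-Protocol rule in 13.1.1 counts missed or late injection visits as under-dosing time, up to the viral load used for the Week 48 Snapshot.
- Section 13.6.5 excludes PK samples affected by bridging from the evaluable set.
- Section 13.11 does not treat permitted bridging as a change in ART.

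The outcome is also named inconsistently. Table 4 (section 7.2.5) gives "<50 copies/mL at Week 48 by delay in IP injection" and marks the analysis exploratory. Section 13.6.4 and Table 2.19 use ≥50 c/mL.

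**The concern.** The display asks whether late dosing goes with virologic failure. For a participant injected at Week 48, the variable is the interval that ended at Week 48. For one not injected, it is an interval that had already closed at the previous injection, so the open gap is never counted and no group exists to hold it.

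In the other direction, an interval in which oral CAB + RPV covered a missed injection gets the same delay as an uncovered miss. The two effects can reverse the intended order. A failure after an uncovered missed injection would read as a failure despite on-time dosing, and a suppressed participant on bridging would read as success despite a long delay. In a table with few late doses and few failures, one misplaced participant can change a row.

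**Working it through.** The SAP gives no figure on this point to reproduce. The check applies its own rules to constructed dosing histories.

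**Inputs**
- Target day for week w is 7w + 1 (13.3.1): Week 36 = 253, Week 40 = 281, Week 44 = 309, Week 48 = 337, Week 52 = 365.
- The Week 48 Snapshot window is Days 295 to 378, Maintenance Phase data only (Table 11).
- Delay formula and groups are as in 13.6.4.
- On-treatment limit: last injection + 35 days, or last oral dose + 1 day if later, applied only to permanent discontinuations (Table 20 and its note 2).
- For participants continuing into the Extension Phase, Maintenance ends at the nominal Week 52 visit (Table 17).

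**How the rule sorts four histories**

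| History | Delay under 13.6.4 | Group |
|---|---|---|
| A. Weeks 40 and 44 on time, Week 48 missed, no bridging | 309 − 281 − 28 = 0 | ≤1 |
| B. Week 44 missed but bridged, Week 48 injected | 337 − 281 − 28 = 28 | >7 |
| C. Week 40 missed but bridged, Week 44 injected, Week 48 missed | 309 − 253 − 28 = 28 | >7 |
| D. Weeks 40 and 44 on time, Week 48 missed but bridged | 309 − 281 − 28 = 0 | ≤1 |

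A and B show the reversal. B gets the same value as an unbridged miss at Week 44. A and D cannot be told apart. In A, an injection at Week 52 would close the open gap at 365 − 309 − 28 = 28 days, group >7.

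**How large the hidden overrun can be in history A**
- Permanent withdrawal without later oral dosing: at most 35 − 28 = 7 days, which belongs to group 4-7.
- Continuing participant with Week 52 on target: at most 365 − 309 − 28 = 28 days.
- Viral load on Day 337 or 338: 0 or 1 day, so the elapsed time still fits ≤1. The groups part only from Day 339 (339 − 309 − 28 = 2).

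**Figures 5.5 and 5.6.** The first is titled "Scatter Plot of Delay in last IP injection by Last Trough CAB Concentration at Week 48 at Maintenance phase"; the second is its RPV counterpart. Under 5.4.2, if the Week 48 pre-dose value is missing, the last earlier pre-dose value is used. That normally pairs a Week 44 trough with the Week 44 delay, which is right. Under 13.3.5, however, a withdrawal, unscheduled or LTFU Month 1 sample can be slotted to Week 48. That trough reflects the time since the Week 44 injection but would be plotted against the delay before it.

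**Outcome.** Snapshot has three classes (13.11): <50, ≥50 and no virologic data. The share not below 50 is therefore the share ≥50 plus the share with no data, and the two versions of the display differ by the latter.

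**The case against.** The strongest reply is that little depends on this table. It is exploratory, descriptive and confined to one arm, with no test or decision rule. That is correct and limits the weight of the point.

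The fallback is also sometimes the right exposure. A viral load around Week 44 (Day 309) lies inside the Snapshot window, and if it is the value used, the Week 44 delay is the interval that preceded it. How often this happens cannot be checked, because the HIV-1 RNA row of the schedule is not legible in the available text. The fix has to preserve this case.

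On bridging, the variable is named as a delay in injection, and 56 days between injections is literally that. Bridging can also be seen in the adherence summary (Table 3.6) and in Listing 63. But a reader of Table 2.19 alone cannot separate covered from uncovered gaps, and a bridged gap counts only if it ends at the injection used.

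Four stronger readings are tempting and are not supported:

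- **A hidden gap of 41 days.** The window alone would allow 378 − 309 − 28 = 41. For a continuing participant that needs a Week 52 visit 378 − 365 = 13 days after target. In addition, HIV-1 RNA is not collected for analysis at Week 52, apart from retests recorded as unscheduled visits (13.2.1).
- **A known dilution of the dosing effect.** The SAP gives no counts of missed or bridged injections, so neither the number mis-sorted nor any bias can be computed.
- **A general fault in Figures 5.5 and 5.6.** Only samples slotted to Week 48 are affected.
- **Replacing the delay by viral load date minus last injection date minus 28.** Suppose the viral load is drawn on the day of a Week 44 injection given 10 days late. The SAP gives 10 days (>7), which is right; the replacement gives 0 − 28 = −28 (≤1), which is wrong.

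**Conclusion.** The point holds for this display. The fallback is explicit in 13.6.4 and Table 2.19. The treatment of bridged gaps follows from the formula, which has no bridging term. An uncovered missed Week 48 injection can be shown as ≤1 day late, while a covered gap that ends at the last injection used is shown as >7 days late.

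The hidden overrun is at most 7 days for permanent withdrawals without later oral dosing, and about 28 days for continuing participants. The 28-day figure assumes the Week 44 injection and the Week 52 visit fall on their target days.

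The <50 versus ≥50 c/mL mismatch is a separate contradiction that needs correcting in any case. The primary and key secondary analyses are unaffected. The point concerns the analysis classification only; no dosing or bridging rule is judged.

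**What to change.** 1. Add to the delay groups in 13.6.4 and Table 2.19 the two categories of 13.6.2: missed injection with, and without, oral bridging.
2. Place there any participant whose Week 48 injection was missed before the Snapshot viral load was taken, and any participant whose last injection interval was bridged.
3. Keep the existing delay of the last injection where the Snapshot viral load was taken on or before the due date of the missed injection. Do not switch to a delay counted from the viral load date.
4. In Figures 5.5 and 5.6, where a trough slotted to Week 48 comes from a withdrawal, unscheduled or LTFU Month 1 sample, plot it against the time since the injection that preceded that sample.
5. Change the Table 4 entry to the ≥50 c/mL outcome, to agree with 13.6.4 and Table 2.19.

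The cost is SAP wording and a small change to one derivation. Injection dates and bridging status are already used elsewhere in the SAP. The drawback is one or two further categories that will probably be sparse.

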13.6.5. Pharmacokinetic

This document is intended for planning analysis of PK concentration data only. Population pharmacokinetics and identification of important determinants of variability will be described in a separate document.

Plasma CAB and RPV concentration-time data

Plasma samples for determination of CAB and RPV concentration will be collected throughout the Maintenance and Extension Phases of the study. Additional samples will be collected for storage during the Long-Term Follow-Up Phase.

Concentration values below the lower limit of quantification (NQ) will be imputed as zero for summary statistics (R&D Guideline: Non-Compartmental Analysis of Pharmacokinetic Data, GUI_51487 (3.0)) and will be denoted as "NQ" in concentration listings.

Evaluable concentration

PK concentration will be summarized in two ways: ‘all data’ without regard to timing relative to scheduled time and ‘evaluable data’.

The ‘evaluable data’ are from the samples that met sample collection window criteria. Sampling windows are set relative to the previous dose as follows:

- 1-5 hours for 2-hour post dose samples;
- ± 3-10 days post last injection for 1-week post injection visits;
- ±4 day for pre-dose sample.
- Samples impacted by dosing errors (wrong dose) or oral bridging will also be excluded

Timepoint	Evaluable window	For Programming:
PRE-DOSE: WK4B/56B only	20-28 hrs after last oral dose taken and the last 3 oral doses administered properly	20 hrs ≤ Days Since Last Oral Dose ≤ 28 hrs and the last 3 oral doses administered on the three consecutive days prior to WK4B/56B.
2-HR-POST:	1-5 hrs	1 hrs ≤ Hours Since Last Injection Dose ≤ 5 hrs
1-WK-POST:	3-10 days post last injection	3 d ≤ Days Since Last Dose ≤ 10 d
PRE-DOSE:	±4 days	24 d ≤ Days Since Last Dose ≤ 32d

Relative Time is calculated relative to the date and time of last previous dose. For example, if the time of the last previous dose (e.g. oral lead-in/oral-bridging) is missing, then the relative time for pre-dose PK sample will be set to missing and the sample will not be considered ‘evaluable’.

If a pre-dose sample is collected on the same day as the first dose of oral bridging, and the time of the first dose (not recorded in eCRF) is confirmed to be ‘after’ the collection of pre-dose sample (by medical monitor or Data querying), then this PK sample will not be impacted by the oral bridging.

At Week 4B/56B, the evaluable window and relative time for 2-HR-POST will be derived based on last injection dose (not the last oral dose). The timing of last oral dose will not affect ‘evaluable’ status with the exception of the last oral dose taken after the 1st injection, i.e. if a subject took the last oral dose after the 1st injection, the 2-HR-POST will not be considered ‘evaluable’, because of the deviation from the IP administration sequence per protocol.

The time-deviation (hours) from the targeted timepoint will be calculated for the samples of ‘2-HR-POST’ and ‘1-Week-POST’ only using the following formula:

Time_deviation (hrs) for ‘2-HR-POST’ =Sample date.time-last previous injection date.time -2 hours

Time_deviation (hrs) for ‘1-Week-POST’ =Sample date.time-last previous injection date.time -7*24 hours

The following windows are for defining 'evaluable' Long-term Follow-up phase PK concentrations.

TIMEPOINT	EVALUABLE WINDOW	FOR PROGRAMMING:
LTFU MONTH 1	± 4 days	24d ≤ Days Since Last Injection ≤ 32d
LTFU MONTH 3	± 1 Week	77d ≤ Days Since Last Injection ≤ 91d
LTFU MONTH 6	± 2 Week	154d ≤ Days Since Last Injection ≤ 182d
LTFU MONTH 9	± 2 Week	238d ≤ Days Since Last Injection ≤ 266d
LTFU MONTH 12	± 2 Week	322d ≤ Days Since Last Injection ≤ 350d

Pharmacokinetic Parameters

- Population pharmacokinetics and identify important determinants of variability will be described in a separate document.

13.6.6. Health Outcome

HIVTSQs

CCI - This section contained Clinical Outcome Assessment data collection questionnaires or indices, which are protected by third party copyright laws and therefore have been excluded.

[figure not shown]
CCI - This section contained Clinical Outcome Assessment data collection questionnaires or indices, which are protected by third party copyright laws and therefore have been excluded.

HIVTSQc

CCI - This section contained Clinical Outcome Assessment data collection questionnaires or indices, which are protected by third party copyright laws and therefore have been excluded.

[figure not shown]
PIN

CCI - This section contained Clinical Outcome Assessment data collection questionnaires or indices, which are protected by third party copyright laws and therefore have been excluded.

Dimension Score (Chevat, 2008)

CCI - This section contained Clinical Outcome Assessment data collection questionnaires or indices, which are protected by third party copyright laws and therefore have been excluded.

CCI - This section contained Clinical Outcome Assessment data collection questionnaires or indices, which are protected by third party copyright laws and therefore have been excluded.

Individual Item Scores

CCI - This section contained Clinical Outcome Assessment data collection questionnaires or indices, which are protected by third party copyright laws and therefore have been excluded.

SF-12

CCI - This section contained Clinical Outcome Assessment data collection questionnaires or indices, which are protected by third party copyright laws and therefore have been excluded.

Dimension Score

CCI - This section contained Clinical Outcome Assessment data collection questionnaires or indices, which are protected by third party copyright laws and therefore have been excluded.

Individual Item Scores

CCI - This section contained Clinical Outcome Assessment data collection questionnaires or indices, which are protected by third party copyright laws and therefore have been excluded.

[figure not shown]
HATQoL (Holmes, 1999)

CCI - This section contained Clinical Outcome Assessment data collection questionnaires or indices, which are protected by third party copyright laws and therefore have been excluded.

Life satisfaction, HIV medications, disclosure worries

[figure not shown]
CCI - This section contained Clinical Outcome Assessment data collection questionnaires or indices, which are protected by third party copyright laws and therefore have been excluded.

CCI - This section contained Clinical Outcome Assessment data collection questionnaires or indices, which are protected by third party copyright laws and therefore have been excluded.

ACCEPT (Acceptance/General Dimension) (Gilet, 2014)

CCI - This section contained Clinical Outcome Assessment data collection questionnaires or indices, which are protected by third party copyright laws and therefore have been excluded.

Tolerability of Injection (NRS)

CCI - This section contained Clinical Outcome Assessment data collection questionnaires or indices, which are protected by third party copyright laws and therefore have been excluded.

Willingness to switch

CCI - This section contained Clinical Outcome Assessment data collection questionnaires or indices, which are protected by third party copyright laws and therefore have been excluded.

Preference question

Questionnaire with one single dichotomous preference question at Week 48 (Q4W IM arm), Week 96 (Current ART arm).

- Assess the treatment preference: Months injection vs daily oral current ART at Week 48 for 'Q4W IM' arm, and at week 96 for 'Current ART' arm who switched to LA.
- Any missing values will remain missing (i.e. no imputation)

